### 8.3.5. Physical Examinations

Physical examination will be listed.

**8.4. Pharmacokinetics Evaluation**

**8.4.1. Concentrations for unchanged edaravone, sulfate conjugate, and glucuronide conjugate**

Plasma unchanged edaravone, sulfate conjugate, and glucuronide conjugate concentrations will be summarized at each nominal sampling point. All plasma concentrations will also be listed. Individual plasma concentrations vs. actual time for unchanged edaravone, sulfate conjugate, and glucuronide conjugate will be plotted on both linear/linear and log/linear scales. Mean plasma concentrations vs. nominal time curves will be plotted on both linear/linear (+SD) and log/linear scales.

**8.4.2. Pharmacokinetic Parameters for unchanged edaravone, sulfate conjugate, and glucuronide conjugate**

The PK parameters listed in Section 2.3 will be calculated for each subject using non-compartmental model. The PK parameters will be listed and summarized. The PK parameters listed as other PK parameters will not be summarized. The urinary pharmacokinetic parameters will be listed and summarized. The urinary pharmacokinetic parameters at pre-dose will not be summarized.

**9. DATA PRESENTATION CONVENTIONS**

**9.1. Number of Digits to Report**

(1) Non-PK related

Statistic	Specification	Apply to
Minimum, Maximum	Same number of DPs as the data provided in the datasets	All original (i.e. non-derived)
	see section 7.3	All derived data
Mean, Median, SD, SE, Confidence intervals	One more DP than above	All
Percentages* 	1 DP	All
Ratios	3 DPs	All

\* Percentages: use 1 place beyond the DP, except for the following cases:

If the percentage is equal to 0, then leave blank, do not use (0)

If the percentage is equal to 100, then use “(100)” without a decimal

(2) PK Plasma Concentration

Statistic	Specification
Individual value	With the number of DP to which they are reported
Mean, SD, Minimum, Median, Maximum	Same number of DPs as the individual value
CV%	1 DP

(3) PK Parameters

Plasma PK Parameters

Statistic	Specification
Individual value	C max : same number of DPs as the plasma concentration t max *: 2 DPs Other parameters to be summarized: number of DPs which the number of significant digits of a minimum parameter is three AUC 0ex : 3 DPs Adjusted R  : 3 DPs Number of Kel points: 0 DP Lower and Upper limited of Kel: 2 DPs
Mean, SD, Minimum, Maximum, Median, Geometric mean	Same number of DPs as the individual values
CV%, Geometric CV%	1 DP

\*: tmax will be expressed basically in terms of median and range

Urine PK Parameters

Statistic	Specification
Individual value	Ae pre-dose , Ae% pre-dose : 3 DPs Other parameters: number of DPs which the number of significant digits of a minimum parameter is three
Mean, SD, Minimum, Maximum, Median, Geometric mean	Same number of DPs as the individual values
CV%, Geometric CV%	1 DP

9.2. Treatments to Report

Treatment	For TFLs
MT-1186	Edaravone

9.3. Analysis Visits to Report

(1) Non-PK related

Safety:

Analysis Visit	Apply to		
	Laboratory Tests	Vital Signs	12-Lead ECGs
Screening	X	X	X
Day -1	X	X	X
Day 1		X	X
Day 2		X	X
Follow up	X	X	X

Screening, unscheduled visits and retests (same visit number assigned) will not be displayed in

by-visit summary tables, but will be included in the data listings.

#### **10. CHANGE FROM THE PROTOCOL**

The listing output of AE is changed from 'Adverse events that occurred will be listed regardless of whether the investigational product was administered' in the protocol to 'All AEs will be listed on the SAF'. The reason to change the output is to enable assessment of safety on SAF instead of assessment on the enrolled subjects.

#### **11. SOFTWARE**

All statistical analyses will be performed using SAS version 9.4 or higher.

The PK parameters will be calculated using WinNonlin® software (version 6.3 or later).

### Appendix 1 Pharmacokinetic Parameter Calculations

- Actual blood sampling times will be used in the calculation of pharmacokinetic parameters
- All concentrations below the LLOQ will be set at zero for pharmacokinetic calculations
- When  $K_{el}$  is missing (or cannot be determined),  $t_{1/2}$ ,  $AUC_{0-\infty}$ ,  $AUC\%_{ex}$ ,  $CL/F$ ,  $MRT$ ,  $V_z/F$  and  $V_{ss}/F$  will not be calculated.

PK Parameter Calculations		
Parameters	Unit	Calculation
$C_{max}$	ng/mL	will be determined by visual inspection
$AUC_{0-\infty}$	ng·h/mL	$AUC_{0-\infty} = AUC_{0-t} + C_{last} / K_{el}$ $C_{last}$ : last measurable concentration
$AUC\%_{ex}$	%	$AUC\%_{ex} = (AUC_{0-\infty} - AUC_{0-t}) / AUC_{0-\infty} \times 100$
$AUC_{0-t}$	ng·h/mL	will be calculated using the linear trapezoidal method and actual times $AUC_{0-t} = \sum_{i=1}^n \frac{t_i - t_{i-1}}{2} (C_{i-1} + C_i)$
$AUC_{0-24}$	h·ng/mL	will be calculated using time until 24 h drug concentration
$t_{max}$	h	Measured time of $C_{max}$
$t_{1/2}$	h	$t_{1/2}$ will be determined as: $t_{1/2} = \log_e(2) / K_{el}$
$K_{el}$	/h	The exponential rate constant of the terminal phase, $k_{el}$ , will be estimated by log-linear regression, if determinable. The number of data points included in the regression will be determined by visual inspection. Wherever possible, a minimum of 3 data points will be used in the estimation of $k_{el}$ .  During the analysis, this calculation method repeats regressions using the last three points with non-zero concentrations, then the last four points, last five, etc. The time of maximum concentration ( $t_{max}$ ) will be excluded from the estimation of $K_{el}$ . Points with a value of zero for the dependent variable are excluded. For each regression, an adjusted $R^2$ is computed $Adjusted R^2 = 1 - \frac{(1 - R^2) \times (n - 1)}{(n - 2)}$ where n is the number of data points in the regression and $R^2$ is the square of the correlation coefficient.

		
The regression with the largest adjusted R^2 is selected to estimate Kel, with these caveats:
 
 
- If the adjusted R^2 does not improve, but is within 0.0001 of the largest adjusted R^2 value, the regression with the larger number of points is used.
 
- kel must be positive, and calculated from at least three data points.
 

CL/F	L/h	$CL/F = \frac{\text{Dose}}{AUC_{0-\infty}}$
MRT	h	$AUMC_{0-\infty} = \sum_{i=1}^n \frac{(t_i - t_{i-1})(t_i \times C_i + t_{i-1} \times C_{i-1})}{2} + \frac{t \times C_t}{K_{el}} + \frac{C_t}{(K_{el})^2}$ $MRT_{0-\infty} = \frac{AUMC_{0-\infty}}{AUC_{0-\infty}}$
V z /F	L	$V_z/F = CL/F \times \frac{1}{K_{el}}$
V ss /F	L	$V_{ss}/F = MRT \times CL/F$
Number of Kel points	-	will be determined using number of points used in computing Kel. If Kel cannot be estimated, zero.
Lower Limit of Kel	h	will be determined using lower limit on time to be included in the calculation of Kel
Upper Limit of Kel	h	will be determined using upper limit on time to be included in the calculation of Kel
Ae	mg	urine concentration × urine volume
Ae%	%	Ae / Dose
CLr	L/h	$CLr = \frac{Ae}{AUC_{0-\infty}}$

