In terms of PK, after a single dose of edaravone solution or suspension in the fasting state, plasma concentrations reached C_{max} 0.3 to 0.4 hours and 0.4 to 0.8 hours after dose, respectively. Subsequently they were excreted in 2 and 3 phases, and $t_{1/2}$ of the terminal phase were 2.4 to 3.2 hours and 5.1 to 11.8 hours, respectively. C_{max} and AUC of edaravone increased more than dose proportional manner over a dose range of 30 to 300 mg. Plasma concentrations of sulfate conjugate and glucuronide conjugate, both are edaravone metabolites, reached C_{max} 0.5 to 1.4 hours and 0.5 to 1.1 hours after dose, respectively. They were excreted from plasma, with $t_{1/2}$ of 4.9 to 7.9 hours and 2.8 to 5.9 hours, respectively. Meal-effect examination after administration of 200 mg suspension (200 mg/10 mL 0.1% polyvinyl alcohol solution) showed that when edaravone was administered 30 minutes after a meal, C_{max} and AUC of plasma edaravone decreased to 18.2% and 39.1% of those when it was administered in the fasting state, respectively. Comparison between plasma concentrations in Caucasian subjects and those in Japanese subjects after administration of 200 mg suspension (200 mg/10 mL) showed that C_{max} and AUC of plasma edaravone in

Confidential

Caucasian subjects were 75% and 79% of those in Japanese subjects, respectively. Five-day multiple doses resulted in no accumulation in plasma concentrations of edaravone.

A clinical pharmacology study of oral edaravone in healthy adult male subjects (as a drug interaction study and as a preliminary study on dosage and administration) (MT-1186-J02 study) is ongoing, and edaravone oral suspension was orally administered to 84 subjects. Drug interaction, safety, and tolerability of 120 mg edaravone oral suspension are being investigated in 66 subjects; and PK, effects of race or meal, safety, and tolerability of 100 mg are being investigated in 18 subjects.

In terms of safety, no serious adverse events occurred. A total of 27 adverse events were observed in 84 subjects. Among them, 7 adverse events (diarrhoea 4, ALT increased 2, and AST increased 1) were assessed as causally related to the administration. All of them were mild in severity and rapidly resolved. No adverse events led to discontinuation in any subject.

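### Does naming both visual inspection and largest adjusted R² for choosing the Kel points leave half-life undefined?

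*SAP*

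**What the plan says.** The Kel row of SAP Appendix 1 deals with the choice of points twice. Its opening paragraph leaves it to the eye: "The number of data points included in the regression will be determined by visual inspection". The next paragraph sets out a search: "During the analysis, this calculation method repeats regressions using the last three points with non-zero concentrations", then the last four, five and so on. Tmax and zero values are left out, each fit gets an adjusted R², and the fit to use is "The regression with the largest adjusted R" squared. If a longer fit comes within 0.0001 of the best, the longer one is taken.

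The minimum also appears twice. Early in the row it is soft: "Wherever possible, a minimum of 3 data points will be used in the estimation of" Kel. At the end it is firm: Kel has to be positive and "calculated from at least three data points".

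The SAP records how each fit was made. The count of points "will be determined using number of points used in computing Kel", and the lower and upper time limits are reported with it; SAP 2.3 adds adjusted R² and AUC%ex. SAP 8.4.2 has these listed by subject, although "The PK parameters listed as other PK parameters will not be summarized".

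Nothing elsewhere ranks the two rules. Protocol 10.1 refers the calculation to the SAP, SAP 8.4.2 names only a non-compartmental approach, and SAP 11 names only the software.

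**The concern.** Pharmacokinetics is the only objective. Kel and t1/2 are endpoints for edaravone and both conjugates, so the choice arises in up to 9 × 3 = 27 profiles; Vz/F is an endpoint for edaravone. Protocol Section 1 (3) 2) describes a three-phase decline after the suspension, with half-lives (solution, then suspension) "of the terminal phase were 2.4 to 3.2 hours and 5.1 to 11.8 hours, respectively". The late samples are at 6, 8, 10, 12 and 24 h. Each earlier point brought into the regression tilts the line toward a faster phase and shortens t1/2.

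If one analyst keeps five points by eye and another follows the algorithm to three, both have complied with the SAP and their half-lives differ. The choice could also be made with the concentrations already in view.

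The two wordings of the minimum add a second doubt. A profile with two usable points would get a Kel under one wording. Under the other it would not, and t1/2, AUC0-∞, CL/F, MRT, Vz/F and Vss/F would then be left uncalculated.

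**Working it through.** The plan states no Kel figure to reproduce, so the check covers the reading of the text and then the size of the effect.

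**1. The two sentences side by side.** The visual sentence gives no criterion. The search gives a starting point, exclusions, a selection statistic, a tie-break and two conditions, and leaves nothing to judgement. The same table describes Cmax too as found by visual inspection, although Cmax is simply the largest measured value. The phrase therefore looks like general wording rather than a rival method.

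**2. The minimum.** The SAP formula is adjusted R² = 1 − (1 − R²)(n − 1)/(n − 2). With n = 2 the divisor is 0, so the algorithm cannot run on two points and the firm minimum is built in. The case is also remote. In the healthy-subject study the suspension peaked at 0.4 to 0.8 h. After 0.8 h there are nine scheduled samples (1, 1.5, 2, 4, 6, 8, 10, 12 and 24 h), so two usable points would mean nothing measurable from 2 h on. The documents give no quantification limit, so this is a judgement of plausibility.

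**3. One profile worked through.** From the documents: sampling times, a 105 mg dose, and a terminal t1/2 of 8 h chosen inside the 5.1 to 11.8 h range. Assumed: earlier half-lives 0.35 and 1.8 h, phase weights 0.93/0.06/0.01, absorption rate 6 /h, scale 2,500 ng/mL, no error. Formulas: t1/2 = ln 2/Kel; AUC0-∞ = AUC0-t + Clast/Kel; CL/F = Dose/AUC0-∞; Vz/F = (CL/F)/Kel.

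| Points (from) | Kel (/h) | t1/2 (h) | Adjusted R² | AUC0-∞ (ng·h/mL) | Vz/F (L) |
|---|---|---|---|---|---|
| 3 (10 h) | 0.1031 | 6.72 | 0.99499 | 1465.3 | 695 |
| 4 (8 h) | 0.1094 | 6.34 | 0.98366 | 1463.5 | 656 |
| 5 (6 h) | 0.1186 | 5.84 | 0.96350 | 1461.3 | 606 |
| 6 (4 h) | 0.1314 | 5.27 | 0.93643 | 1458.7 | 548 |

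The algorithm picks three points. Forcing five gives t1/2 5.84/6.72 = 0.87 and Vz/F 606/695 = 0.87, both 13% lower. AUC0-∞ is 1461.3/1465.3 = 0.997, or 0.3% lower.

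**4. Forced fits over a wider range.** The grid has 3 × 3 × 3 = 27 scenarios: terminal t1/2 5.1, 8 or 11.8 h; terminal phase 5, 10 or 20% of AUC; intermediate t1/2 1, 1.5 or 2 h. Also assumed: intermediate phase 35% of AUC, first phase 0.3 h, 10% error, 24 h sample measurable. Against the algorithm, median t1/2 was 0–15% shorter with four points and 6–34% shorter with five. With five points Vz/F fell 6–34%, MRT 0–11% and Vss/F 0–10%. AUC%ex fell 6–34% in relative terms, which is small in absolute terms (2.08% to 1.81% in step 3). AUC0-∞, CL/F and CLr moved by about 1% at most.

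**5. What a visual reader would do.** Step 4 imposes fits; it does not model inspection. In 24 of the 27 scenarios the 6 h value lies about 70% or more above the terminal line, where a reader would be expected to drop it. In the other three it lies at most about 52% above; there the four-point median ratio was 1.000 and the five-point t1/2 was 6–16% shorter. Inspection was then modelled directly: start from the last three points and add an earlier one only if it lies within 20–30% of the fitted line. The median t1/2 ratio to the algorithm stayed within about 2% in every scenario. With the 30% limit, t1/2 shifted by more than 10% in 1–25% of profiles, depending on the scenario.

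**The case for a change.** The best case for amending the SAP is that no sentence ranks the two rules, the protocol leaves the method to the SAP, and listing the points afterwards is not the same as fixing them beforehand. A ranking clause would be cheap. In all 27 scenarios the forced four- and five-point fits lay further below the true half-life than the algorithm did, so an analyst who overreached by eye would do worse.

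Part of this stands. The precedence clause is missing, the soft and firm minimum are loosely drafted, and single profiles can differ by more than 10%.

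The size does not stand. The 6–34% range describes five-point fits that neither the algorithm nor a careful reader would usually choose. Nor does the obvious amendment remove the judgement. Making the algorithm primary, with overrides allowed for a written reason, leaves the reader as free as before unless it also sets a criterion for overriding and says which value is summarised. It would write down the natural reading without supplying a better estimator. With no comparator or test, there is also no planned contrast that the choice could favour.

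**Conclusion.** This is a drafting gap that analysts fill sensibly, and no change to the plan follows. The row contains a full algorithm, and visual inspection sits naturally beside it as a check. Under a reasonable visual rule the two agree to within about 2% on median t1/2. The disagreement that remains falls on single profiles, mainly in Kel, t1/2, Vz/F and AUC%ex, with less on MRT and Vss/F. Cmax and AUC0-t do not use Kel, and AUC0-∞, CL/F and CLr move by about 1%.

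The study describes nine patients without a hypothesis test, so no error rate depends on the choice. The number of points, time limits and adjusted R² are listed for each profile, and SAP 8.4.1 provides individual log-scale plots, so any fit can be reconstructed. At this sample size the listing does the work that a summary of these diagnostics would do.

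The sizes rest on assumed profiles. Only the terminal half-life range, the dose and the sampling times come from the documents, and that range is from healthy men given 30 to 300 mg. The conjugates were not modelled separately. The figures illustrate the effect and do not bound it; the reading of the text does not depend on them.

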and reduced body weight gain and a decrease in food consumption were observed at the minimum toxic dose in rats; however, these changes were relieved or disappeared after withdrawal from the drug. In dogs, salivation, sedation, blinking, sneezing, and hind limb weakness were observed in a transient manner.

In a 2-week multiple oral dose study, the NOAEL was 300 mg/kg/day in rats, 30 mg/kg/day in female dogs, and 100 mg/kg/day in male dogs. In rats, toxicological changes were observed only in the 1,000 mg/kg/day group, and were similar to those seen after rapid IV injection. Forestomach erosion, prolonged activated partial thromboplastin time, and submandibular gland acinar cell hypertrophy were observed as toxicological changes after an oral dose but not after rapid IV injection. In dogs, toxicological changes were observed in females in the ≥ 100 mg/kg/day groups and males in the 300 mg/kg/day group, and were similar to those seen after rapid IV injection.

In a 24-hour continuous IV administration study in dogs, neurologic manifestations (e.g., limited limb movement, muscle hypotonia) were observed in the 14-day 120 and 300 mg/kg/day groups, with the earliest onset shown on Day 12 of administration. Histopathological manifestations were peripheral and spinal nerve fiber degeneration. The NOAEL in neurotoxicity was 300 mg/kg/day for 5-day administration, 120 mg/kg/day for 10-day administration, and 60 mg/kg/day for 14-day administration. In a regimen of 5-day administration followed by 4-week interruption in the 24-hour continuous IV administration study in dogs, it has been indicated that the manifestations in the peripheral nerve tissue may be reversible due to the interruption.

At the NOAEL, there were no findings of clinical importance in other toxicity studies, as well.

The PK assessment in rats showed that AUC correlated well with the dose for IV administration. Edaravone was metabolized fast. The major metabolites were glucuronide conjugate and sulfate conjugate, which were excreted in the urine. The urinary excretion of the unchanged drug was approximately 1% of the dose. Regarding the sulfate conjugate and glucuronide conjugate, neither a radical scavenging effect nor a lipid peroxidation inhibitory effect have been observed.

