In an in vitro assay using human kidney homogenates, after deconjugation of the sulfate conjugate, edaravone was suggested to be re-conjugated with glucuronic acid and excreted mainly as the glucuronide conjugate in the urine. Multiple uridine diphosphate glucuronyl transferases (UGTs), including UGT1A9 were involved the glucuronidation reaction. Edaravone was bound to human serum proteins at a ratio of 91% to 92% (primarily to albumin).

Edaravone increased mRNA expression of CYP1A2, CYP2B6, and CYP3A4 in human hepatocytes, indicating its inducing effect on P-450 isozymes. Both direct and time-dependent inhibitory effects of edaravone were strongest on CYP2C9 among each P-450 molecular species in human hepatic microsomes, with IC_{50} of 84.5 $\mu\text{mol/L}$ and 44.8 $\mu\text{mol/L}$ (shifted IC_{50}), respectively. Edaravone, its sulfate conjugate, and its glucuronide conjugate showed no inhibitory effects on metabolic activities of UGT1A1 and UGT2B7 in human hepatic microsomes. Edaravone showed inhibitory effects on BCRP and OAT3, both of which are drug transporters, with IC_{50} of 121 $\mu\text{mol/L}$ and 72.3 $\mu\text{mol/L}$, respectively. Edaravone sulfate conjugate showed OAT1 and OAT3 inhibitory effects with IC_{50} of 13.6 $\mu\text{mol/L}$ and 2.74 $\mu\text{mol/L}$, respectively.

Confidential

2) Clinical Study Results

Thus far, the following clinical studies of edaravone (injection) have been performed: 6 clinical pharmacology studies in healthy adult subjects in Japan and Europe; 8 clinical studies in patients with acute phase of cerebral infarction in Japan, Europe, and South Korea, 3 clinical studies in patients with subarachnoid hemorrhage in Japan; and, 5 clinical studies in patients with ALS in Japan.

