7.1 Name of the Investigational Product

Edaravone oral suspension (MT-1186): A white to brown aqueous suspension containing 105 mg of edaravone drug substance powder in 5 mL of edaravone oral suspension.

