9.2.4 Pharmacokinetic assessments

Blood sampling will be performed for measurement of plasma concentrations of unchanged edaravone, sulfate conjugate, and glucuronide conjugate, and urine sampling will be performed for measurement of urine concentrations of them. The investigator (or subinvestigator) or study collaborator will record the dates and times of the blood and urine sampling and the sampled urine volume in the CRF. The measurement will be conducted in the drug concentration measurement site.

If any other assessments are scheduled at the same time point of blood sampling for plasma drug concentration measurement, blood sampling will be performed at the exact scheduled time point, and other assessments will be performed before or after the blood sampling. In principle, a 12-lead ECG and vital signs (except for body temperature) will be measured before the blood sampling for plasma drug concentration measurement and safety assessment. Urine will be forced to void 24 hours after administration. Urine will not be collected from subjects if collection is difficult.

The acceptable time range for the time of each blood or urine sampling (forced void) will be

Confidential

specified in a separate document.

9.2.4.1 Measurement of plasma concentrations of unchanged edaravone, sulfate conjugate, and glucuronide conjugate

Time points and volume of blood sampling

(a) Time points of blood sampling

Day 1	Before investigational product administration, 0.083, 0.25, 0.5, 0.75, 1, 1.5, 2, 4, 6, 8, 10, and 12 hours after administration
Day 2	24 hours after investigational product administration

(b) Frequency of blood sampling: 14

(c) Volume of blood sampling: 5.5 mL, Total: 77 mL (per subject)

9.2.4.2 Measurement of urine concentrations of unchanged edaravone, sulfate conjugate, and glucuronide conjugate

Urine volume will be measured at voiding and the urine specimen will be processed (see Section 9.2.4.3). Urine will be forced to void before administration and 24 hours after administration. Urine will not be collected from subjects if collection is difficult.

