10.1 Pharmacokinetic(s)

Plasma concentrations of unchanged edaravone, sulfate conjugate and glucuronate conjugate will be measured to calculate AUC_{0-t} , AUC_{0-24} , $AUC_{0-\infty}$, C_{max} , t_{max} , $t_{1/2}$, Kel , MRT ,* CL/F ,* V_z/F ,* and V_{ss}/F * by non-compartmental analysis (*: calculate only for unchanged edaravone). Urine concentration will be measured to calculate Ae , $Ae\%$, and CL_r/F * (*: calculate only for unchanged edaravone). The detailed calculation method for each parameter will be described in the Statistical Analysis Plan.

The drug concentration measurement site will separately create a protocol for concentration measurement by the start of measurement and perform measurement according to it. The site will create a measurement result report.

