### 2.3. Pharmacokinetic Assessments

- (1) Drug concentration (in plasma and urine)

Unchanged edaravone, sulfate conjugate, and glucuronide conjugate

- (2) Pharmacokinetic parameters

Unchanged edaravone:  $AUC_{0-t}$ ,  $AUC_{0-24}$ ,  $AUC_{0-\infty}$ ,  $C_{max}$ ,  $t_{max}$ ,  $t_{1/2}$ ,  $Kel$ ,  $MRT$ ,  $CL/F$ ,  $V_z/F$ ,  $V_{ss}/F$ ,  $Ae$ ,  $Ae\%$ ,  $CLr$

Sulfate conjugate and glucuronide conjugate:  $AUC_{0-t}$ ,  $AUC_{0-24}$ ,  $AUC_{0-\infty}$ ,  $C_{max}$ ,  $t_{max}$ ,  $t_{1/2}$ ,  $Kel$ ,  $Ae$ ,  $Ae\%$

(t: Final concentration measurable time point)

Other PK parameters (for all PK profiles for which the  $Kel$  has been calculated):  $AUC\%_{ex}$ , Adjusted  $R^2$ , Number of  $Kel$  points, Lower limited of  $Kel$ , Upper limiter of  $Kel$

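### Does one Ae% formula for edaravone and both conjugates misstate the conjugates' share of the dose?

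*SAP*

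**What the plan says.** Protocol 10.1 divides the work between two documents. On the parameters: "The detailed calculation method for each parameter will be described in the Statistical Analysis Plan". On the assay: "The drug concentration measurement site will separately create a protocol for concentration measurement", due by the start of measurement and followed by a report of the results.

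SAP 2.3 names the analytes in plasma and urine as unchanged edaravone, "sulfate conjugate, and glucuronide conjugate", and lists Ae and Ae% for all three. SAP 8.4.2 has the urinary parameters listed and summarised.

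Appendix 1 of the SAP has one row for each quantity, with no version by analyte:

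- Ae, unit mg: "urine concentration × urine volume".
- Ae%, unit %: Ae over dose, with no factor of 100 and no molecular-weight term.

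The denominator is edaravone itself. Protocol 7.1 describes the product as a suspension "containing 105 mg of edaravone drug substance powder in 5 mL of edaravone oral suspension". The urine subsection of Protocol 9.2.4, headed "Measurement of urine concentrations of unchanged edaravone, sulfate conjugate, and glucuronide conjugate", gives no unit or reporting basis. The abbreviation lists of both documents define Ae and Ae% in terms of drug excreted, without saying whether that means the parent or the analyte measured.

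**The concern.** A conjugate molecule is heavier than the edaravone molecule inside it. If the laboratory reports milligrams of conjugate, Appendix 1 divides milligrams of one substance by milligrams of another, and the quotient is not a share of the dose. It is too high by a constant that differs between the two conjugates, so their Ae% values could be neither compared nor added as shares of the dose.

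The conjugate lines may also be the ones that carry most of the urinary recovery. In the non-clinical part of Protocol Section 1, the rat result reads: "The urinary excretion of the unchanged drug was approximately 1% of the dose". An assay in human kidney homogenates suggested that edaravone is "excreted mainly as the glucuronide conjugate in the urine". Neither is human excretion data, but both point the same way.

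The percent sign without a multiplication by 100 adds to the impression of a formula written in haste, because the AUC%ex row of the same table does show it.

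**Working it through.** The documents state no value of Ae or Ae%, so there is no figure to reproduce. The check is one of units and scale.

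**Inputs from the documents.** Dose 105 mg of edaravone (Protocol 7.1 and 8.3); Ae in mg and Ae% = Ae / Dose (SAP Appendix 1).

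**Assumed inputs.** The documents give no molecular weights. Take a parent weight M of 174.2 g/mol, with a range of 150 to 250; the sulfate adds 80.06 and the glucuronide adds 176.12.

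**Formula.** Let f be the true molar share of the dose recovered as a given conjugate.

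- Edaravone equivalents: Ae = f × 105 mg, so Ae / Dose = f. The factor is 1.00 for both conjugates.
- Conjugate mass: Ae = f × 105 mg × (conjugate weight / M), so Ae / Dose = f × (conjugate weight / M).

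**Factors on conjugate mass.**

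| Parent weight M | Sulfate | Glucuronide | Glucuronide / sulfate |
|---|---|---|---|
| 150 | 230.06/150 = 1.534 | 326.12/150 = 2.174 | 1.418 |
| 174.2 | 254.26/174.2 = 1.460 | 350.32/174.2 = 2.011 | 1.378 |
| 250 | 330.06/250 = 1.320 | 426.12/250 = 1.704 | 1.291 |

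**Illustration.** The 60% here is invented. If 60% of the dose left as glucuronide and results were conjugate mass, Ae would be 105 × 0.60 × 2.011 = 126.7 mg, and Ae / Dose would be 126.7 / 105 = 120.7%. With the factor 2.011, any true share above 1/2.011 = 49.7% would print as more than 100% of the dose and expose itself. A smaller share would not.

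**Reach.** In SAP 2.3 the conjugates have AUCs, Cmax, tmax, half-life, Kel, Ae and Ae%. Of these, only Ae% sets a conjugate amount against a parent amount. CL/F, the volumes and CLr are planned for edaravone alone. CV% and geometric CV% do not change when every value is multiplied by a constant. The reach is therefore the conjugate Ae% lines, together with the question of whether conjugate Ae in mg means conjugate or parent.

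**Notation.** With Ae = 1.05 mg, Ae / Dose = 1.05/105 = 0.01, which in the stated unit is 1%; the factor of 100 follows from the unit column. The table is equally terse elsewhere. CL/F and CLr divide mg by ng·h/mL and are reported in L/h, and 1 mg / (1 ng·h/mL) = 10^6 mL/h = 1000 L/h, so a factor of 1000 is also unwritten.

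**The case for a change.** The best case for a change is that Protocol 10.1 gives the calculation of each parameter to the SAP, and turning a conjugate concentration into a percentage of an edaravone dose is a calculation. The unwritten factors of 100 and 1000 can be recovered from the unit column, but the concentration basis cannot, because mg fits both readings. A second programmer working from Appendix 1 alone could not tell whether a conversion is due. In a descriptive pharmacokinetic study the tabulated parameters are the result, and one sentence would settle the matter.

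The facts in this stand. Neither document states the basis, and a molecular-weight ratio is less obvious from the units than a factor of 100. The inference to a faulty plan does not stand. Whether a result is in conjugate mass or parent equivalents is decided by the assay, and Protocol 10.1 sends the assay to its own protocol and report. Nobody computes Ae% from Appendix 1 alone: the urine concentrations have to be taken from those results, with their unit and basis. The definitions in terms of drug excreted, and the single Ae row set against an edaravone dose, fit an edaravone-equivalent reading, though they do not prove it. In a table that leaves routine conversions unwritten, a missing ratio is weak evidence that a needed one would be left out.

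The possible harm is also narrow. The plan lists and summarises each analyte separately. It does not compare the two conjugates' Ae% or add them to a total recovery, and it tests no hypothesis.

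**Conclusion.** The plan leaves the concentration basis of the conjugates unstated, but nothing in the documents shows the Ae% formula to be wrong. On edaravone equivalents it is exact once the factor of 100, implied by the unit, is applied. On conjugate mass, conjugate Ae% would be too high by about 1.46 (sulfate; 1.32 to 1.53) and 2.01 (glucuronide; 1.70 to 2.17). These factors rest on assumed molecular weights and are not an estimate of bias in this trial.

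No change follows. A change would only write down a basis that the analysts must already have from the measurement results. If the conversion were ever missed, one constant per conjugate would restore the share of dose without new data. Edaravone's own Ae, Ae% and CLr do not depend on the point. The conclusion assumes that the separate measurement protocol, which could not be checked here, fixes the basis; on its purpose as given in Protocol 10.1, that is a reasonable expectation.
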